**[name]**  
Senior Research Scientist  
Department of Research

February 15, 2019

Dear Clinicaltrials.gov administration,

This cover letter accompanies a protocol being submitted for NCT02998372. The study is supported by an NIH grant (R21 AR069150). The study primarily focuses on computational simulation of function for knees with patellar instability. For validation of the models, simulated data was compared to pre-operative and post-operative measures of patellar tracking and patellofemoral contact pressures determined by computational reconstruction of functional activities performed by patients during MRI scans. Prior to the proposed study, imaging with accompanying kinematics, pressure data and computational models was available for seven subjects being treated for patellar instability. The grant application proposed adding 5 additional subjects and models to the study. Because the subjects would be evaluated pre-operatively and post-operatively, the study was designated as a clinical trial, although the surgical approach was left up to the surgeon as opposed to being specified within the protocol. Therefore, the study was registered on clinicaltrials.gov based on the aims and goals listed for the grant application.

Patient enrollment has now been completed for the study. Only three of the proposed five subjects that were to be evaluated pre-operatively and post-operatively were enrolled. Additional pre-operative imaging from other sources was used to complete creation of the necessary number of models.

The attached protocol is an abbreviated version of the NIH grant application that includes the development of computational models and the analysis of the five subjects. That is the clearest document to describe the relationship between the clinical trial portion of the study and the overall stated goals.

Please let me know if you have any questions about this document.

Sincerely,

A handwritten signature in black ink that reads "[name]".

[name]

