### 2. Characterize influence of surgical stabilization on knee function for individual patients

The multibody dynamic models will be used to simulate MPFL reconstruction and tibial tuberosity medialization. MPFL reconstruction will be simulated with variations in the femoral attachment position, while the magnitude of tuberosity realignment will be varied. The actual surgical procedures performed on the patients will be simulated, with the influence on lateral tracking and contact patterns compared to in vivo results to validate simulation of the surgical procedures.

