### 3. Compare surgical options as a function of patellofemoral anatomy

Variations in patellar tracking and contact pressure will be compared between MPFL reconstruction and tuberosity medialization. Techniques to alter trochlear dysplasia and tuberosity lateralization will also be developed and applied to the models. Simulations performed while varying anatomy will establish ranges over which each surgical option limits patellar maltracking without elevating contact pressures.

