High resolution MRI scans of subjects with patellar instability are currently available for 7 subjects from a previous study (3T scanner, extremity coil, proton density-weighted images, sagittal plane, 0.3 mm in plane resolution, 1.5 mm slice thickness). Models will be reconstructed from these scans, allowing representation of cartilage surfaces and attachment points for the ligaments, patellar tendon, and quadriceps tendon. Five additional subjects scheduled for surgical stabilization for recurrent patellar instability will be recruited to meet the proposed sample size of 12 models.

The 5 recruited subjects will participate in pre-operative computational reconstruction of in vivo knee function with closed chain loading conditions. The technique uses high resolution MRI scans to create computational models of the femur, patella and tibia, as well as the cartilage. Low resolution scans are acquired during isometric quadriceps contraction with the knee positioned at multiple flexion angles, with the aid of a MRI-compatible loading frame that applies a spring-loaded force of 60 N to 85 N along the axis of the body at the foot. Shape matching algorithms align models of the bones from the high resolution images, with attached cartilage, to bones reconstructed from lower resolution scans with the knee flexed.

Models of each knee will be used to simulate the in vivo function. The muscle forces will be ramped up until the

reaction force at the foot reaches the spring force applied in vivo. A direct comparison of tibiofemoral and patellofemoral kinematics and contact pressures between computational and in vivo data will be performed. The accuracy of computational simulation will be reported in terms of root mean square errors between the computational and in vivo data, along with correlation coefficients evaluating the accuracy of variations in output related to changing the flexion angle and between knees. Once the pre-operative models are validated by comparison to the output from reconstruction of in vivo function, they will be used to represent a dynamic squatting

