### **Aim 3: Compare surgical options**

The simulation models will be used to represent two primary surgical options: reconstruction of the medial patellofemoral ligament and realignment of the tibial tuberosity, while also varying parameters related to knee anatomy. The kinematics and pressure output from all the simulated surgical variations will be compared between the 12 models at individual degrees of knee flexion with repeated measures ANOVA's combined with post-hoc Student-Newman-Keuls tests, with significance set at  $p = 0.05$ . The analyses will focus on relative variations in the kinematics and pressure measurements, with the pre-operative condition treated as the control for each knee, with the goal of each procedure to reduce lateral patellar shift and tilt without increasing the contact pressure.

Analyses will be performed for various combinations of tibial tuberosity position and depth of the trochlear groove. For each combination, the statistical analyses noted above will be performed to compare the influence of the various surgical procedures on patellar tracking and contact, with an emphasis on determining the limits at which each procedure becomes ineffective in reducing lateral tracking without overloading cartilage. In addition, for each procedure multivariable linear regression analyses will be performed to relate the anatomical parameters to the change in the output parameters.

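### The Aim 3 regression leaves out the surgical levels that the plan varies, so its tuberosity-position coefficient for medialization is easy to misread

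*Combined protocol and SAP*

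**What the plan says.** Tuberosity position appears in two roles.

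- **As surgery.** Specific Aim 2: "MPFL reconstruction will be simulated with variations in the femoral attachment position, while the magnitude of tuberosity realignment will be varied".
- **As anatomy.** Specific Aim 3: "Techniques to alter trochlear dysplasia and tuberosity lateralization will also be developed and applied to the models". Approach, Aim 3: "Analyses will be performed for various combinations of tibial tuberosity position and depth of the trochlear groove".

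Approach, Aim 3 then sets out two analyses. The first is a repeated measures ANOVA with post-hoc tests across all the simulated surgical variations. It is repeated for each anatomical combination, and the limits of each procedure are to be found from it. The second is supplementary: "for each procedure multivariable linear regression analyses will be performed to relate the anatomical parameters to the change in the output parameters". The reference for change is the same knee before surgery.

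The text does not say how realignment magnitudes are chosen, whether tuberosity position means the native or the post-operative position, whether surgical levels are pooled in the regression, or whether limits will be reported by magnitude.

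**The concern.** The regression names anatomical predictors only, although the plan also varies a surgical level within each procedure. Two consequences follow.

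First, if levels are pooled, variation caused by the magnitude (or by the attachment position) is counted as residual error. The anatomical coefficients become less precise and describe an average over whichever levels were simulated.

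Second, medialization moves the same structure that the anatomical variation moves. If both act along the medial-lateral axis, a knee at position L medialized by d is in the same state as the unoperated knee at L − d. The coefficient on L in a model for change then measures how the slope of the response differs between L and L − d. It does not measure how strongly tuberosity position drives tracking. A small coefficient could be taken to mean that tuberosity position does not matter for medialization, while the maltracking left after surgery still rises with L.

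At stake is the interpretation of Aim 3, which seeks the anatomical ranges over which each option limits maltracking.

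**Working it through.** **Inputs from the documents.** The only relevant figure is the number of models: 7 existing plus 5 to be recruited gives 12 ("High resolution MRI scans of subjects with patellar instability are currently available for 7 subjects from a previous study"; "Five additional subjects scheduled for surgical stabilization for recurrent patellar instability will be recruited to meet the proposed sample size of 12 models"), and it adds up. The documents give no response slope, grid of positions, magnitudes or error SD. All millimetre values and slopes below are assumptions for illustration, not proposals.

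**Algebra.** Let f(L) be an output such as lateral shift at tuberosity position L, larger being worse. After medialization by d the output is f(L − d). The reduction is R = f(L) − f(L − d).

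- Linear, f = bL: R = bd, which does not contain L.
- Curved, f = bL + γL²: R = bd + γ(2Ld − d²), so the slope of R on L is 2γd, averaged over d.

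**Illustration.** L = 10, 15, 20, 25 and d = 5, 10, 15, fully crossed (12 states, no noise), b = 0.4. With mean d = 10 and γ = ±0.01, the expected slope is 2 × (±0.01) × 10 = ±0.20. Least squares gives:

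| Response | Slope of R on L | R² with L only | R² with L, d, L×d | Slope of post-operative output on L |
|---|---|---|---|---|
| 0.4L | 0.00 | 0.00 | 1.00 | 0.40 |
| 0.4L + 0.01L² | +0.20 | 0.19 | 0.998 | 0.55 |
| 0.4L − 0.01L² | −0.20 | 0.50 | 0.994 | 0.25 |

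In the linear case R runs from 0.4 × 5 = 2 to 0.4 × 15 = 6 purely because of d. In all three rows a more lateral tuberosity leaves a worse post-operative output, yet the coefficient for the reduction is zero, positive or negative.

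**How far the near-zero result extends.** A second simulation used 12 knees, positions 10 to 22 mm, groove depths 1, 3 and 5 mm, slope 0.5 and error SD 0.5, all assumed. The coefficient of the reduction on native position, by how the magnitude is set, was:

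| Response | Fixed d = 10 | d = 5, 10, 15 crossed | d set to reach position 10 |
|---|---|---|---|
| Linear | 0.00 | 0.00 | 0.50 |
| Threshold | 0.43 | 0.37 | 0.43 |
| Quadratic | 0.40 | 0.40 | 0.64 |

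The near-zero coefficient therefore needs both a roughly linear response and a magnitude that does not depend on native position. In the linear crossed case, adding d raised R² from about 0.00 to 0.94 and recovered the assumed effect of 0.50 per mm.

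**Collinearity.** Final position = L − d. With a constant, native position, magnitude and final position have rank 3 of 4, so they cannot all enter one model. If every knee is moved to one target T, then d = L − T exactly, and magnitude cannot be separated from native position.

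**Limits.** Suppose a limit were defined as the native position at which the post-operative output reaches a cutoff. With output 0.5 × position − 0.8 × groove depth, depth 3 and an assumed cutoff of 2.0, the limit is (2.0 + 2.4)/0.5 + d = 8.8 + d, that is 13.8, 18.8 and 23.8 mm for d = 5, 10 and 15. A limit of this kind moves 1 mm per mm of medialization.

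**The case against.** The case on the other side is substantial.

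- **Limits.** A reader might infer that no limit will be tied to a magnitude. The documents do not support that. Limits come from the ANOVA, not the regression. The ANOVA takes in all simulated surgical variations, so magnitudes may already be levels. What stands is narrower: no sentence says that limits will be reported by magnitude.
- **Near zero by construction.** A reader might infer that the design forces the medialization coefficient to zero. It does not, as the second table shows. The plan looks for limits beyond which a procedure stops reducing lateral tracking. Under exact linearity the reduction would be constant and no such limit would exist, so the aim itself presupposes some non-linearity.
- **Estimand.** The plan concentrates on change relative to the pre-operative knee. For that quantity a zero slope is a correct answer. The one-for-one shift in limits uses a residual-output criterion with a cutoff that the documents do not contain.
- **Same axis.** The techniques for altering lateralization are still to be developed, and nothing says they are the exact inverse of medialization.
- **Pooling.** Fitting the regression separately by level would be compatible with the wording.
- **Comparing coefficients.** A reader might infer that coefficients will be compared between medialization and MPFL reconstruction. Nothing says so; the ANOVA makes that comparison.
- **Abbreviation.** The cover letter calls the protocol a shortened grant application, so detail may have been cut.

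These points limit the claim. They do not supply a surgical level in the regression as stated, or a definition of native versus post-operative position.

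**Conclusion.** The concern holds in a limited form. The plan varies a surgical level within each procedure, also varies tuberosity position as anatomy, and specifies a supplementary regression of change on anatomy alone.

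If levels are pooled, the loss can be large: in the assumed examples, R² is 0.00 to 0.50 without the surgical level and at least 0.99 with it and its interaction. The near-zero position coefficient for medialization is conditional on a shared axis, a roughly linear response, and a magnitude that does not depend on native position. When it occurs it is right about change and uninformative about residual maltracking.

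The sizes are illustrative, because the documents give no response curve or grid. The point concerns interpretation and efficiency of a secondary analysis; it does not invalidate the ANOVA or the limits drawn from it.

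**What to change.** In Approach, Aim 3:

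1. Define native (or altered) and final tuberosity position, and state how realignment magnitudes are set.
2. Add the surgical level to each procedure's regression (realignment magnitude for medialization, femoral attachment position for MPFL reconstruction) with its interaction with tuberosity position, or fit the regression separately by level.
3. For medialization, regress post-operative output on final tuberosity position in a separate model, because native position, magnitude and final position are collinear.
4. State whether magnitudes are ANOVA levels, and report each medialization limit with the magnitude to which it applies.
5. State that the coefficient of change on native position is not to be read as evidence that tuberosity position does or does not matter for post-operative tracking.

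If the magnitude is set to reach a target position, item 2 cannot separate it from native position; only items 3 and 4 then apply. With a single target the final position is also constant, so the model in item 3 would need more than one target, or the unoperated states included, to be estimable.

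The cost is small, since the simulations are already planned: a few more parameters with 12 knees, and a less compact statement of the limits. No realignment magnitude is proposed here.
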